#### **9.6.2 Blood Collection for Serum MK-4280**

Sample collection, storage and shipment instructions for serum samples will be provided in the procedure and/or laboratory manuals.

#### **9.6.3 Blood Collection for Anti-MK-1308 Antibodies**

Sample collection, storage and shipment instructions for serum samples will be provided in the procedure and/or laboratory manuals. Anti-MK-1308 antibody samples should be drawn according to the ADA collection schedule for participants who receive MK-1308 in combination with pembrolizumab. Simultaneous PK sampling is required for interpretation of ADA analysis.

#### **9.6.4 Blood Collection for Anti-MK-4280 Antibodies**

Sample collection, storage and shipment instructions for serum samples will be provided in the procedure and/or laboratory manual. Anti-MK-4280 antibody samples should be drawn according to the ADA collection schedule for participants who receive MK-4280 in combination with pembrolizumab. Simultaneous PK sampling is required for interpretation of ADA analysis.

#### **9.7 Pharmacodynamics**

Pharmacodynamic markers will be evaluated to gain a better understanding of response and resistance biology. Tumor biopsy will be performed at baseline (archival tissue acceptable for this sample). Blood samples for exploratory biomarkers and planned genetic analysis will be collected prior to treatment on C1D1, C2D1, C3D1, C6D1, and at end of treatment/progression. Detailed endpoints are described below in the biomarker section (Section 9.9).

#### **9.8 Future Biomedical Research Sample Collection**

The following specimens are to be obtained as part of Future Biomedical Research:

- DNA for future research
- Leftover RNA
- Leftover tumor

#### **9.9 Biomarkers**

To identify novel biomarkers, the following biospecimens to support exploratory analyses of cellular components (e.g., protein, RNA, DNA, metabolites) and other circulating molecules will be collected from all participants in this study as specified in the SoA. Sample collection, storage, and shipment instructions for the exploratory biomarker specimens will be provided in the laboratory manual.

- Blood for Genetic Analysis
- Blood for RNA analyses
- Whole blood for DNA for exploratory biomarkers
- Archival or newly obtained tumor tissue

##### **9.9.1 Planned Genetic Analysis Sample Collection**

Sample collection, storage and shipment instructions for Planned Genetic Analysis samples will be provided in the Procedures manual. The planned genetic analysis sample should be drawn for planned analysis of the association between genetic variants in DNA and drug response. Whole blood for planned genetic analysis will be collected at C1D1 for DNA and RNA and at C2D1, C3D1, C6D1 and end of therapy for RNA only. This sample will not be collected at the site if there is either a local law or regulation prohibiting collection, or if the IRB/IEC does not approve the collection of the sample for these purposes.

### **9.9.2 Enrollment Biomarkers**

A tumor specimen for biomarker assessment will be required for enrollment of all participants. A new tumor specimen (defined as a tumor specimen collected since the completion of the most recent cancer therapy), if obtained as part of normal clinical practice (not solely for the purpose of screening for enrollment in this study), is preferred to archival samples. If collection of such a new tumor specimen for this study would require a procedure, not otherwise clinically indicated, that would create significant risk for the participant (including, but not limited to, biopsies of the brain, lung/mediastinum, pancreas, or endoscopic procedures extending beyond the esophagus, stomach, or bowel), an archival specimen should be submitted.

Archived tissue (or fresh biopsy) is required at screening for GEP and TMB testing. These tests are required for enrollment. Sample collection, storage and shipment instructions are provided in the procedure manual.

### **9.9.3 PD-L1 IHC**

Archived tissue (or fresh biopsy) is required at screening. Part of this sample will be used for retrospective testing of PD-L1 IHC. Sample collection, storage and shipment instructions are provided in the procedure manual. Historical PDL-1 results may be used with Sponsor approval.

### **9.9.4 Exploratory Biomarkers**

Archived tissue (or fresh biopsy) is required at screening for GEP, TMB, and PD-L1 IHC testing. Residual tissue will be used for exploratory biomarker assays.

Whole blood will be collected for planned genetic analysis and exploratory biomarkers. Whole blood samples for nucleic acid will be collected at C1D1, C2D1, C3D1, C6D1, and end of the treatment.

Tissue and blood sample collection, storage and shipment instructions are provided in the procedure manual.

## **9.10 Visit Requirements**

Visit requirements are outlined in Section 2 – Schedule of Activities (SoA). Specific procedure-related details are provided above in Section 9 – Study Assessments and Procedures.

### **9.10.1 Screening**

Approximately 28 days prior to treatment allocation/randomization, potential participants will be evaluated to determine that they fulfill the entry requirements as set forth in Section 6.1.

Written consent must be obtained prior to performing any protocol-specific procedure. Results of a test performed prior to the participant signing consent as part of routine clinical management are acceptable in lieu of a screening test if performed within the specified time frame. Screening procedures are to be completed within 28 days prior to the first dose of study treatment except for the following:

- Laboratory tests are to be performed within 10 days prior to the first dose of study treatment. An exception is HIV and hepatitis testing, which may be done up to 28 days prior to the first dose of study treatment.
- Evaluation of ECOG is to be performed within 7 days prior to date of allocation/randomization.
- For women of reproductive potential, a urine or serum pregnancy test will be performed within 72 hours prior to the first dose of study treatment. If urine pregnancy results cannot be confirmed as negative, a serum pregnancy test will be required (performed by the local study-site laboratory).
- Archival tumor sample collection is not required to be obtained within 28 days prior to the first dose of study treatment. Newly obtained tumor tissue may be obtained within 90 days of treatment initiation.

Participants may be rescreened after initially failing to meet the inclusion/exclusion criteria. Screening procedures may be repeated after consultation with the Sponsor. Rescreening should include all screening procedures listed in the protocol SOA, including consent review. Results from assessments during the initial screening period are acceptable in lieu of a repeat screening test if performed within the specified time frame and the corresponding inclusion/exclusion criteria is met. Participants who are rescreened will retain their original screening number.

### **9.10.2 Treatment Period**

Visit requirements are outlined in the Study Flow Chart (Section 2). Specific procedure-related details are provided in Section 9.1.

### **9.10.3 Post-Treatment Visit**

#### **9.10.3.1 Safety Follow-up Visit**

The mandatory Safety Follow-up Visit should be conducted approximately 30 days after the last dose of study treatment or before the initiation of a new anticancer treatment, whichever comes first.

#### **9.10.3.2 Efficacy Follow-Up Visits**

Participants who complete the protocol-required cycles of study treatment or who discontinue study treatment for a reason other than disease progression will begin Efficacy Follow-Up and should be assessed approximately every 12 weeks by radiographic imaging to monitor disease status. The Sponsor may request survival status to be assessed at additional time points during the course of the study (not to exceed approximately 12 weeks). Every effort should be made to collect information regarding disease status until the start of new anti-cancer therapy, disease progression, death, end of study as detailed in Section 2 (SoA).

Information regarding post-study anticancer treatment will be collected if new treatment is initiated. Participants who completed all efficacy assessments and/or will not have further efficacy assessments must enter Survival Follow-up.

Once a participant has been consented for the extension study, radiographic imaging will be collected as instructed in the extension study.

#### **9.10.3.3 Survival Follow-up Assessments**

Participant survival follow-up status will be assessed approximately every 12 weeks to assess for survival status until death, withdrawal of consent, or the end of the study, whichever occurs first.

The first survival follow-up assessment should be scheduled as described below:

1. For participants who discontinue study treatment and who will not enter Efficacy Follow-up, the first survival follow-up contact will be scheduled 12 weeks after the Discontinuation Visit and/or Safety Follow-up Visit (whichever is last).
2. For participants who completed assessments in Efficacy Follow-up, the first survival follow-up contact will be scheduled 12 weeks after the last efficacy assessment follow-up visit has been performed.

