## Table 2 Study Flow Chart – Pembrolizumab + MK-4280

Study Period	Screen Phase	Treatment Period Cycle = 21 Days							EO T	Posttreatment Visits			Notes
Visit		C1 D1	C2 D1	C3 D1	C4 D1	C5 D1	C6 D1	C7 and Beyond	Dis-con	Safety Follow-up	Follow-up	Survival Follow-up	
Scheduling Window:	-28 to -1 d	+3 d	±3 d	±3 d	±3 d	±3 d	±3 d	±3 d	At Dis-con	30 d Post Discon +14 d	Q12W ±7 d	Q12W ±7 d	
Administrative Procedures													
Informed Consent Form	X												If the investigator plans to treat beyond disease progression, additional consent is required.
Future Biomedical Research ICF	X												This is optional for the participant.
Inclusion/Exclusion Criteria	X												
Participant ID Card	X												
Demographics and Medical History	X												
Prior/Concomitant Medications	X	X	X	X	X	X	X	X	X	X	X		
NSCLC Disease Details and Prior Treatment	X												
Subsequent Antineoplastic Therapy Status									X	X	X	X	
Survival Status		←────────────────────────────────→								←──────────→		X	After Investigator determines PD or start of new anticancer treatment. In addition, upon Sponsor request, participants may be contacted for survival status at any time during the course of the study.

Study Period	Screen Phase	Treatment Period Cycle = 21 Days							EO T	Posttreatment Visits			Notes
Visit		C1 D1	C2 D1	C3 D1	C4 D1	C5 D1	C6 D1	C7 and Beyond	Dis-con	Safety Follow-up	Follow-up	Survival Follow-up	
Scheduling Window:	-28 to -1 d	+3 d	±3 d	±3 d	±3 d	±3 d	±3 d	±3 d	At Dis-con	30 d Post Discon +14 d	Q12W ±7 d	Q12W ±7 d	
Clinical Procedures/Assessments													
Review Adverse Events	X	X	X	X	X	X	X	X	X	X	X		If Discon visit ≥30 days from last dose of study treatment, Safety Follow-up Visit is not required. SAEs followed for 90 days post-treatment.
Full Physical Examination	X												To be performed within 7 days prior to start of study treatment.
Directed Physical Examination		X	X	X	X	X	X	X	X	X			
Vital Signs and Weight	X	X	X	X	X	X	X	X	X	X			Vital signs (VS) to include temperature, pulse, respiratory rate, and blood pressure for all participants. VS to be done prior to the administration of each infused study treatment. VS also performed 2 and 4 hr post infusion for MK-4280 for C1 D1.
Height	X												
12-Lead ECG	X	X	X	X					X	X			At indicated times and when clinically indicated.
MUGA or ECHO LVEF assessment	X												
Assess NYHA cardiac disease classification	X												

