## Table 3 Study Flow Chart – Pembrolizumab + Lenvatinib

Study Period	Screen Phase	Treatment Period Cycle = 21 Days							EOT	Posttreatment Visits			Notes
Visit		C1 D1	C2 D1	C3 D1	C4 D1	C5 D1	C6 D1	C7 and Beyond	Dis-con	Safety Follow-up	Follow-up	Survival Follow-up	
Scheduling Window:	-28 to -1 d	+3 d	±3 d	±3 d	±3 d	±3 d	±3 d	±3 d	At Dis-con	30 d Post Discon +14 d	Q12W ±7 d	Q12W ±7 d	
Administrative Procedures													
Informed Consent Form	X												If the investigator plans to treat beyond disease progression, additional consent is required.
Future Biomedical Research ICF	X												This is optional for the participant.
Inclusion/Exclusion Criteria	X												
Participant ID Card	X												
Demographics and Medical History	X												
Prior/Concomitant Medications	X	X	X	X	X	X	X	X	X	X	X		
NSCLC Disease Details and Prior Treatment	X												
Subsequent Antineoplastic Therapy Status									X	X	X	X	
Survival Status												X	After Investigator determines PD or start of new anticancer treatment. In addition, upon Sponsor request, participants may be contacted for survival status at any time during the course of the study.

Study Period	Screen Phase	Treatment Period Cycle = 21 Days							EOT	Posttreatment Visits			Notes
Visit		C1 D1	C2 D1	C3 D1	C4 D1	C5 D1	C6 D1	C7 and Beyond	Dis-con	Safety Follow-up	Follow-up	Survival Follow-up	
Scheduling Window:	-28 to -1 d	+3 d	±3 d	±3 d	±3 d	±3 d	±3 d	±3 d	At Dis-con	30 d Post Discon +14 d	Q12W ±7 d	Q12W ±7 d	
Clinical Procedures/Assessments													
Review Adverse Events	X	X	X	X	X	X	X	X	X	X	X		
If Discon visit ≥30 days from last dose of study treatment, Safety Follow-up Visit is not required. SAEs followed for 90 days post-treatment. SAEs followed for 120 days post-treatment for participants treated with lenvatinib.
 
Participants in the lenvatinib group will be contacted by telephone or have a visit on C1D8 ± 3d to assess for development of early toxicity. An unscheduled visit can occur prior to C1D15 ± 3d if deemed necessary by the investigator

Full Physical Examination	X												
To be performed within 7 days prior to start of study treatment. The physical exam must include an oral exam.

Study Period	Screen Phase	Treatment Period Cycle = 21 Days							EOT	Posttreatment Visits			Notes

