#### **7.2.1.1 Dose Modification and Toxicity Management for Immune-related AEs Associated with Pembrolizumab Monotherapy, Coformulations or IO Combinations**

AEs associated with pembrolizumab monotherapy, coformulation, or IO combination exposure may represent an immune-related response. These irAEs may occur shortly after the first dose or several months after the last dose of pembrolizumab monotherapy, coformulation, or IO combination treatment and may affect more than one body system simultaneously. Therefore, early recognition and initiation of treatment is critical to reduce complications. Based on existing clinical study data, most irAEs were reversible and could be managed with interruptions of pembrolizumab monotherapy, coformulation, or IO combination administration of corticosteroids and/or other supportive care. For suspected irAEs, ensure adequate evaluation to confirm etiology or exclude other causes. Additional procedures or tests such as bronchoscopy, endoscopy, skin biopsy may be included as part of the evaluation.

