### **9.3.1 Time Period and Frequency for Collecting AE, SAE and Other Reportable Safety Event Information**

All AEs, SAEs and other reportable safety events that occur after the consent form is signed but before treatment allocation/randomization must be reported by the investigator if the participant is receiving placebo run-in or other run-in treatment, if the event cause the participant to be excluded from the trial, or is the result of a protocol-specified intervention, including but not limited to washout or discontinuation of usual therapy, diet, or a procedure.

- All AEs from the time of treatment allocation/randomization through 30 days following cessation of study treatment must be reported by the investigator.
- All AEs meeting serious criteria, from the time of treatment allocation/randomization through 90 days following cessation of study treatment, or 30 days following cessation of study treatment if the participant initiates new anticancer therapy, whichever is earlier must be reported by the investigator. For participants treated with lenvatinib, all AEs meeting serious criteria, from the time of treatment allocation/randomization through 120 days following cessation of study treatment, or 30 days following cessation of study treatment if the participant initiates new anticancer therapy, whichever is earlier must be reported by the investigator.
- All pregnancies and exposure during breastfeeding, from the time of treatment allocation/randomization through 120 days following cessation of study treatment, or 30 days following cessation of study treatment if the participant initiates new anticancer therapy must be reported by the investigator.
- Additionally, any SAE brought to the attention of an investigator at any time outside of the time period specified above must be reported immediately to the Sponsor if the event is considered to be drug-related.

Investigators are not obligated to actively seek AE or SAE or other reportable safety events in former study participants. However, if the investigator learns of any SAE, including a death, at any time after a participant has been discharged from the study, and he/she considers the event to be reasonably related to the study treatment or study participation, the investigator must promptly notify the sponsor.

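### Participants who stop for progression and start no new therapy have no scheduled enquiry for new SAEs over the last 46 to 60 days of the 90-day reporting window (76 to 90 of 120 days for lenvatinib)

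*Combined protocol and SAP*

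**What the plan says.** **Reporting window.** Section 9.3.1 has SAEs reported "through 90 days following cessation of study treatment, or 30 days following cessation of study treatment if the participant initiates new anticancer therapy"; the shorter of the two periods applies. For lenvatinib it reads "For participants treated with lenvatinib, all AEs meeting serious criteria, from the time of treatment allocation/randomization through 120 days following cessation of study treatment", with the same 30-day cut. Table 3 repeats this as a note: "SAEs followed for 120 days post-treatment for participants treated with lenvatinib". Neither the section nor the note ties a visit or call to day 90 or day 120.

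**Scheduled AE review.** In Tables 2 and 3 the Review Adverse Events row is marked from screening through treatment, Discontinuation, Safety Follow-up and the Follow-up column, and is blank under Survival Follow-up. The same row of Table 1 (MK-1308) is not legible in the text available for this review.

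**Safety Follow-up Visit.** Section 9.10.3.1 calls it mandatory and has it "conducted approximately 30 days after the last dose of study treatment or before the initiation of a new anticancer treatment, whichever comes first". The flow chart gives "30 d Post Discon +14 d" and adds: "If Discon visit ≥30 days from last dose of study treatment, Safety Follow-up Visit is not required".

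**After that.** Under Section 9.10.3.2 only completers and participants who stop for a reason other than progression enter Efficacy Follow-up. For those who stop for documented progression, the discontinuation scan is the last one required (Section 9.2.1.3). Section 9.10.3.3 then sets when they are next contacted: "the first survival follow-up contact will be scheduled 12 weeks after the Discontinuation Visit and/or Safety Follow-up Visit (whichever is last". The flow charts set survival contacts every 12 weeks, ±7 days.

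**The concern.** A duty to report SAEs to day 90 or 120 works only if someone asks. For a participant who stops for progression, the schedule stops asking at about day 30 to 44, and the next planned contact is a survival call that is not marked for AE review. Section 7.2.1.1 itself warns about late events: "These irAEs may occur shortly after the first dose or several months after the last dose of pembrolizumab monotherapy". Section 9.3.3 does require proactive follow-up, but only after an event has been reported, and at later visits or contacts.

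Two things are at stake. One is the completeness of late SAE data for the combinations. The other is even ascertainment: a participant who stops for toxicity or completes treatment is questioned again at Efficacy Follow-up, and one who stops for progression is not. Detection of late SAEs would then depend on the reason for stopping, which may differ between combinations.

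**Working it through.** The plan states no figure of its own here, so this is calendar arithmetic on its windows. Day 0 is the last dose, taken first to coincide with discontinuation.

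**Inputs**
- SAE window: 90 days, or 120 for lenvatinib; 30 if new anticancer therapy starts (Section 9.3.1).
- Safety Follow-up Visit: day 30 to 30 + 14 = 44 (flow charts).
- Survival contact: 84 ± 7 days after the later of the Discontinuation and Safety Follow-up Visits (Section 9.10.3.3 and flow charts).

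**1. First survival contact after progression**
- Earliest: 30 + 84 − 7 = day 107.
- Nominal: 30 + 84 = day 114.
- Latest: 44 + 84 + 7 = day 135.

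This is always after day 90. For lenvatinib it may fall before or after day 120.

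**2. SAE window left after the last scheduled AE review**

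| Arm | Review on day 44 | Review on day 30 |
|---|---|---|
| 90-day window | 90 − 44 = 46 days (51%) | 90 − 30 = 60 days (67%) |
| Lenvatinib, 120-day window | 120 − 44 = 76 days (63%) | 120 − 30 = 90 days (75%) |

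**3. Safety Follow-up waived.** The Discontinuation Visit is then on day 30 or later and carries its own AE review. If it falls on day 30, the next call is 30 + 84 ± 7 = day 107 to 121, and 60 (or 90) days remain. A later visit leaves less of the window and moves the call later.

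**4. New anticancer therapy started.** The window ends at day 30, so after a day-30 visit 30 − 30 = 0 days remain. There is no gap.

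**5. Stopped for another reason.** An Efficacy Follow-up review every 84 ± 7 days, counted from discontinuation, falls on day 77 to 91.

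**6. Sensitivity to the anchor.** Suppose the Discontinuation Visit is 21 days after the last dose (an assumption) and the flow-chart anchor is used. Safety Follow-up is then on day 51 to 65 from last dose, and the survival call on day 107 + 21 = 128 to 135 + 21 = 156. The uncovered part is 90 − 65 = 25 to 90 − 51 = 39 days, or 120 − 65 = 55 to 120 − 51 = 69 days for lenvatinib. The gap is shorter, but the call comes later.

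**7. Size of the group.** Let p be the share of discontinued participants who stop for progression and q the share of those who start new therapy. The affected share is p(1 − q). The documents give neither. With p assumed at 40% to 80% and q at 0% to 60%, it runs from 0.4 × 0.4 = 16% to 0.8 × 1 = 80%.

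**The case against.** The other side has real points.

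- **Reporting does not depend on the schedule alone.** SAE reporting through the window is mandatory, and drug-related SAEs are reportable at any time (Section 9.3.1). Hospitalizations and emergency room visits are recorded to day 90 (Section 9.11), and medications taken for SAEs after the Safety Follow-up Visit (Section 7.7.1). So a reader who infers that late SAEs are left to chance goes too far. But none of these provisions schedules a contact at which a new event would come to light.
- **Contact is not wholly absent.** Lenvatinib-arm participants subject to pregnancy testing are tested at least every 30 days to day 120 or new therapy (Table 3, Section 9.5.5.2). The sponsor may also ask for survival status at any time (Section 9.10.4). The first reaches only part of one arm, the second is discretionary, and neither is an AE review.
- **The waiver.** One might infer that participants coming off a long toxicity hold lose their review. They do not: if they stop for toxicity they enter Efficacy Follow-up, and the Discontinuation Visit has its own AE review.
- **The endpoints.** One might infer a biased secondary endpoint. Events after stopping cannot change the number discontinuing due to AEs. A missed late SAE changes the number of participants with AEs only if that participant had no earlier AE. Safety is summarized descriptively (Section 10.6.2), and nothing shows that reasons for stopping will differ by arm.
- **A call after day 90 is not in itself a fault.** It could still elicit an earlier event, but only if the question is asked, and Tables 2 and 3 do not ask it.

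**Conclusion.** The point holds for participants who stop for progression and start no new anticancer therapy. Followed as written, the schedule has no enquiry for new SAEs over 46 to 60 of 90 days, or 76 to 90 of 120 days for lenvatinib. The next planned contact, at day 107 to 135, is not marked for AE review. Those figures assume that discontinuation and last dose coincide; a later Discontinuation Visit shifts them as in step 6 of the working.

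The missing AE entry is established for Tables 2 and 3 only. The timing rule in Section 9.10.3.3 applies to all arms, but the AE row for MK-1308 needs checking in the original.

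It would be tempting to say that most discontinued participants are affected. The documents do not support that: the 30-day cut removes everyone who starts new therapy, and an assumed range of 16% to 80% settles nothing. This is a gap in scheduled ascertainment of late SAEs, worth closing because it is cheap to close. It is not evidence that the safety endpoints are invalid.

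**What to change.** 1. In Tables 2 and 3, mark an SAE enquiry at the first Survival Follow-up contact. Do the same in Table 1 if it is blank there.
2. In Section 9.10.3.3, time that contact to the close of the SAE window counted from last dose: day 90 +7, or day 120 +7 for lenvatinib. Apply this to participants not in Efficacy Follow-up, including where the Safety Follow-up Visit is waived.
3. Keep the 30-day limit once new anticancer therapy starts.
4. Reconcile Section 9.10.3.1 (mandatory, counted from last dose) with the flow charts (waivable, counted from discontinuation).

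The cost is one re-timed telephone call that is already planned, an added question, and somewhat more SAE reports to process. In the lenvatinib arm the call could fall up to 127 − 30 = 97 days after the Safety Follow-up Visit, against 84 + 7 = 91 now, so the first contact needs its own window entry. Later survival contacts can stay at 12-week intervals.
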